7.1. Treatment Administered

This study involves a comparison of once-weekly SC dose levels of LY3298176 (2.5 mg to 10 mg titration regimen for Cohort 1, 5 mg to 15 mg titration regimen for Cohort 2, and 5 mg fixed dose for Cohort 3) with corresponding volume-matched placebo. [Table GPGC.2](#) shows the treatment regimens.

Each vial of the IMP will contain 5 mg of LY3298176, will be reconstituted in sterile water for injection (Japan Pharmacopeia), and will be administered subcutaneously. Doses will be dispensed in accordance with the randomization scheme provided by the sponsor. Patients assigned to placebo treatment will receive SC injections of normal saline with the volume matching the LY3298176 at each dose level. Please refer to the IMP Operation/Handling Procedure for detailed instructions.

All injections will be administered into the SC tissue of the abdominal wall. Injection sites will be alternated weekly between 4 sites on the abdominal wall (ie, right and left upper quadrants and right and left lower quadrants).

Whenever possible, IMP administration should be carried out by the same personnel. Dosing will commence at approximately the same time of day in all dose cohorts. The actual time of dosing will be recorded in the patient's electronic case report form (eCRF).

Table GPGC.2. Treatments Administered

Dose level	Number of vial	Volume per injection (mL)	Number of injection	Total volume of injection (mL)
LY 2.5 mg/PL	1	0.5	1	0.5
LY 5 mg/PL	1	1.0	1	1.0
LY 10 mg/PL	2	1.0	2	2.0
LY 15 mg/PL	3	1.0	3	3.0

Abbreviations: LY = LY3298176; PL= placebo.

The investigator or designee is responsible for:

- explaining the correct use of the IMP to the site personnel,
- verifying that instructions are followed properly,
- maintaining accurate records of IMP dispensing and collection,
- returning all unused medication to Lilly or its designee at the end of the study.

7.1.1. Packaging and Labeling

Investigational medicinal products for this study are as follows:

- LY3298176 will be provided in a vial, which will be provided in a carton.
- Placebo will be provided as sodium chloride (saline) in a vial.

The IMP will be labeled according to the country's regulatory requirements.

7.2. Method of Treatment Assignment

Randomization tables for allocation of LY3298176 or placebo will be prepared by the statistician for the study and provided to the site pharmacists involved in dose preparation. The allocation and dispensing of the IMP will be fully documented and verified by a second person. Detailed records of the amounts of the IMP received, dispensed, and remaining at the end of the study will be maintained by the site pharmacist.

7.2.1. Selection and Timing of Doses

The doses will be administered at approximately the same times on each day. The actual time of all dose administrations will be recorded in the patient's eCRF.

7.3. Blinding

The dosing regimen is patient- and investigator-blind. To preserve the blinding of the study, all study site personnel, except pharmacy staff who prepare and dispense study medication, will be blinded to treatment allocation.

Blinding will be maintained until the database is locked with data up to Day 85 (blinded period) as described in the separate Blinding Plan ([Appendix 8](#)).

The site pharmacist who prepares and dispenses study medication will receive a randomization table with treatment codes to enable preparation of blinded placebo doses. The pharmacist will assign treatment.

Emergency codes will be available to the investigator. A code, which reveals the treatment group for a specific study patient, may be opened during the study only if the patient's well-being requires knowledge of the patient's treatment assignment.

If a patient's study treatment assignment is unblinded during the blinded period, the patient must be discontinued from the study unless the investigator obtains specific approval from a Lilly clinical pharmacologist, CRP, or CRS for the study participant to continue in the study. During the study, emergency unblinding should occur only by accessing the study patient's emergency code.

In case of an emergency, the investigator has the sole responsibility for determining if unblinding of a patient's treatment assignment is warranted for medical management of the event. The patient's safety must always be the first consideration in making such a determination. If the investigator decides that unblinding during the blinded period is warranted, it is the responsibility of the investigator to promptly document the decision and rationale and notify Lilly as soon as possible.

Upon completion of the study, all codes must be returned to Lilly or its designee.

For the blinded items in the clinical laboratory tests, please refer to [Appendix 2](#).

7.4. Dose Modification

If the investigator decides not to up-titrate the dose level of IMP at Days 15, 29, or 43 in the titration regimen for individual patients in Cohorts 1 or 2 for the reason of safety and/or tolerability, patients may keep current dose level to the planned last dose at Day 50 and will no longer be allowed up-titration during the treatment period. Down-titration is not allowed during the treatment period for any patients in Cohorts 1, 2, or 3.

The planned highest dose of Cohort 2, 15 mg LY3298176, may be reduced to 12.5 mg before to the first patient visit of Study GPGC if the first interim analysis of the ongoing Phase 2 Study I8F-MC-GPGB indicates that the 15 mg dose is not well tolerated.

7.4.1. Dose Escalation

The dose escalation decision will be made on the basis of the safety data at the 10-mg dose level of Cohort 1 to proceed to Cohort 2. The safety data up to Day 36 (predose procedure) of Cohort 1 from at least 8 patients (to include at least 5 on LY3298176) will be reviewed.

Safety data will be the primary criteria for the dose escalation. In addition, if available at the time of dose-escalation decision, PK results may be used as supporting data for dose escalation. No dose decision can occur without prior discussion and agreement between the investigator and the Lilly clinical pharmacologist, CRP, or CRS.

Safety data, in particular AEs, SAEs, and adverse laboratory abnormalities, will be independently assessed by the investigator and will be considered related to the IMP unless there is clear evidence that the event is not related.

After review of these data, an agreement on the appropriate dose will be made by the investigator and sponsor for Cohort 2.

The planned dosing regimen of Cohort 2 may be changed to 2.5 mg for Days 1 and 8; followed by 5 mg for Days 15 and 22; and 8 mg for Days 29, 36, 43, and 50, or the corresponding volume-matched placebo before the first dose of Cohort 2 if the safety assessment for the dose-escalation decision indicates that the 10-mg dose of Cohort 1 is not well tolerated.

If any of the following scenarios occur, dosing at the current level and dose-escalation from Cohort 1 to Cohort 2 will be discontinued:

- 1) if a single patient experiences an SAE other than anticipated pharmacology of LY3298176 (for example, GI-related AEs [particularly nausea, vomiting, and diarrhea] or hypoglycemia)
- 2) two clinically significant events (CSEs) in each cohort that are related to LY3298176 administration, with the exception of anticipated pharmacology of LY3298176
- 3) if 50% or more of patients in a cohort experience a symptomatic hypoglycemic episode with plasma/serum glucose levels of ≤ 3.0 mmol/L [54 mg/dL])

- 4) if more than 4 patients in 1 cohort experience moderate treatment-related AEs that impair normal activities
- 5) if 2 or more patients experience an acute pancreatitis event ([Appendix 6](#))

Examples of unrelated events could include but are not limited to: events occurring before LY3298176 dosing; events experienced after receiving placebo; personal injury accidents that were not a result of hemodynamic changes or neurological symptoms (dizziness, visual disturbance, numbness, loss of muscle control); events resulting from viral or bacterial infections; or changes in clinical chemistry or liver enzymes as a result of documented acute viral hepatitis, alcohol, or other hepatotoxic drug use.

A CSE will be determined by the investigator or suitable designee ([Appendix 4](#)) and may include findings that do not fulfill the criteria for SAEs. Patients experiencing CSEs thought to be related to the IMP will be encouraged to complete a 28-day follow-up period before study discharge.

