Informed consent	X						
Distribution of glucose meters, test strips, and diaries/SMPG training	X ^e	X					
7-point SMPG		X ^f					
Medical history	X						
Physical examination	X						
Medical assessment	X			X	X	X	
AEs/concomitant medications	X			X	X	X	X
Chest x-ray ^g	X						
Height and weight	X						
Body temperature	X						
Vital signs (BP/PR) ^{h,i}	X			X	X	X	
12-Lead ECG ^{i,j}	X			X	X	X	
PK sampling ^{k,l}				X	X	X	X
Clinical safety lab (hematology, chemistry, urinalysis) ^{m,n}	X			X	X	X	
Clinical safety lab (serology) ⁿ	X						
Pregnancy test (serum, urine) ^{n,o,p}	X						
Follicle-stimulating hormone ^{n,o}	X						
Urine drug and alcohol screen ^{n,p}	X						
Hemoglobin A1c ^{l,m}	X						
Fasting glucose, insulin, glucagon ^{l,m}				X	X	X	
Immunogenicity ^l					X	X	X

Study Schedule Protocol I8F-JE-GPGC Cohort 1 for Treatment Period

Procedure	Treatment Period (Cohort 1)																					
	-1	1	2	3	4	8	15	16	17	18	22 ±1	29	30	31	32	36 ±1	43 ±1	50	51	52	57	ET1 ^d
Inpatient stay at CRU ^q	X	X	X	X	X		X	X	X	X		X	X	X	X		X	X	X			
Outpatient visits to CRU						X					X					X	X				X	X
Remind Patients about 7-point SMPG						X					X					X				X		
7-point SMPG							X					X					X				X	
Randomization		X																				
IMP administration ^r		X				X	X up-titra- tion				X	X up-titra- tion				X	X	X				
Medical assessments		Pre	X	X	X	X	X	X	X	X	X	X	X	X	X	X	X	X	X	X	X	
AEs/concomitant medications	X	X	X	X	X	X	X	X	X	X	X	X	X	X	X	X	X	X	X	X	X	
Weight ^t		Pre				Pre	Pre				Pre	Pre				Pre	Pre	Pre			X	X
Body temperature	X	Pre																				X
Vital signs (BP/PR) ^{h,i}	X	Pre, 1, 4, 8, 12	24	48	72	Pre	Pre	24	48	72	Pre	Pre	24	48	72	Pre	Pre	Pre			168	X
12-Lead ECG ^{i,j}		Pre, 8	24	48	72	Pre	Pre				Pre	Pre				Pre	Pre	Pre,	8	24	168	X
PK sampling ^{k,l}		Pre, 8	24	48	72	Pre	Pre				Pre	Pre				Pre	Pre	Pre,	8	24	48	168
Clinical safety lab (hematology, chemistry, urinalysis) ^{m,n}	X		24	48		Pre	Pre	24	48		Pre	Pre	24	48		Pre	Pre	Pre	24	48	168	X
OGTT ^{l,u}	X																			X		
Hemoglobin A1c ^{l,m}		Pre										Pre									168	X
Fasting glucose, insulin, glucagon ^{l,m}		Pre	24			Pre	Pre	24			Pre	Pre	24			Pre	Pre	Pre	24 ^v		168	X
Meal intake and appetite ^w	L/D		L/D																L/D			
Lipid panel ^{l,m,x}		Pre									Pre								24			X

Study Schedule Protocol I8F-JE-GPGC Cohort 1 for Treatment Period

Procedure	Treatment Period (Cohort 1)																				
	-1	1	2	3	4	8	15	16	17	18	22 ±1	29	30	31	32	36 ±1	43 ±1	50	51	52	57

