Exploratory storage samples ^{l,m,y}		Pre				Pre												24			X
Pharmacogenetic sample ^l		Pre																			
Nonpharmacogenetic sample (storage) ^{l,m}		Pre					Pre					Pre				Pre	Pre			168	X
Immunogenicity ^l		Pre									Pre									168	X

Study Schedule Protocol I8F-JE-GPGC Cohort 2 for Treatment Period

Procedure	Treatment Period (Cohort 2)																					
	-1	1	2	3	4	8	15	16	17	18	22 ±1	29 ±1	36 ±1	43	44	45	46	50	51	52	57	ET1 ^d
Inpatient stay at CRU ^q	X	X	X	X	X		X	X	X	X				X	X	X	X	X	X	X		
Outpatient visits to CRU						X	X				X	X	X	X							X	X
Remind Patients about 7-point SMPG						X					X		X								X	
7-point SMPG							X					X		X								X
Randomization		X																				
IMP administration ^r		X				X	X up-titra- tion				X	X	X	X up-titra- tion				X				
Medical assessments		Pre	X	X	X	Pre	Pre	X	X	X	Pre	Pre	Pre	Pre	X	X	X	Pre	X	X	X	
AEs/concomitant medications	X	X	X	X	X	X	X	X	X	X	X	X	X	X	X	X	X	X	X	X	X	
Weight ^t		Pre				Pre	Pre				Pre	Pre	Pre	Pre				Pre			X	X
Body temperature	X	Pre																				X
Vital signs (BP/PR) ^{h,i}	X	Pre, 1, 4, 8, 12	24	48	72	Pre	Pre	24	48	72	Pre	Pre	Pre	Pre	24	48	72	Pre			168	X
12-Lead ECG ^{i,j}		Pre, 8	24	48	72	Pre	Pre				Pre	Pre	Pre	Pre				Pre, 8	24		168	X
PK sampling ^{k,l}		Pre, 8	24	48	72	Pre	Pre				Pre	Pre	Pre	Pre				Pre, 8	24	48	168	X
Clinical safety lab (hematology, chemistry, urinalysis) ^{m,n}	X		24	48		Pre	Pre	24	48		Pre	Pre	Pre	Pre	24	48		Pre	24	48	168	X
OGTT ^{l,u}	X																				X	
Hemoglobin A1c ^{l,m}		Pre									Pre										168	X
Fasting glucose, insulin, glucagon ^{l,m}		Pre	24			Pre	Pre	24			Pre	Pre	Pre	Pre	24			Pre	24 ^v		168	X
Meal intake and appetite ^w	L/D		L/D															L/D				
Lipid panel ^{l,m,x}		Pre									Pre							24				X

Study Schedule Protocol I8F-JE-GPGC Cohort 2 for Treatment Period

Procedure	Treatment Period (Cohort 2)																					
	Days	-1	1	2	3	4	8	15	16	17	18	22 ±1	29 ±1	36 ±1	43	44	45	46	50	51	52	57
Exploratory storage samples ^{l,m,y}		Pre				Pre													24			X
Pharmacogenetics sample ^l		Pre																				
Nonpharmacogenetic sample (storage) ^{l,m}		Pre					Pre					Pre		Pre				Pre			168	X
Immunogenicity ^l		Pre									Pre										168	X

Study Schedule Protocol I8F-JE-GPGC Cohort 3 for Treatment Period

Procedure	Treatment Period (Cohort 3)															ET1 ^d
	-1	1	2	3	4	8	15 ±1	22 ±1	29 ±1	36 ±1	43 ±1	50	51	52	57	
Days																
Inpatient stay at CRU ^q	X	X	X	X	X							X	X	X		

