- d The patient who discontinues from the study between Day 1 to Day 57 inclusive will complete ET1 procedures as soon as possible. And then, the patient will be asked to complete ET2 procedures after a washout period of at least 28 days from the last IMP administration. The patient who discontinues from the study after the completion of Day 57 will complete ET2 procedures after a washout period of at least 28 days from the last IMP administration.
- e Patients who were taking metformin or DPP-IV inhibitors (except for omarigliptin, trelagliptin, and linagliptin) at screening will be required to monitor their plasma glucose levels during the 28-day washout period.
- f Patients will conduct the 7-point SMPG from the distribution of glucose meters until the day before Day -1.
- g Patients who have completed chest x-ray within the past 12 months and whose x-ray and/or report are available for review are exempt from the chest x-ray examination.
- h Refer to Section 9.4.2 for instructions on vital signs.
- i Vital signs and ECGs should be scheduled before, but as close as possible to the PK sample times. Scheduled meals should occur after ECG/vital signs measurement.
- j Refer to Section 9.4.3 for instructions on ECGs. Patients must be supine for approximately 5 to 10 minutes before ECG collection and remain supine but awake during ECG collection. A single local safety ECG will be measured at screening and Day 85 (follow-up) or ET visit. The Day 1 predose ECG will be taken in triplicate every 15 minutes for 1 hour (-60, -45, -30, and -15 min) to establish a baseline. At the other visits, ECGs will be collected in triplicate at the specified time points. ECGs must be recorded before collecting any blood for safety or PK samples and as close as possible to the time of the blood draw.
- k PK sampling for LY3298176 on Day 1 at predose, 8 and 24 (Day 2), 48 (Day 3), 72 (Day 4), and 168 (Day 8) hours after the first dose (168-hour sample to be collected before the second dose of LY3298176). Additional PK samples to be collected at predose on Days 15, 22, 29, 36, and 43, and on Day 50 at predose, 8 and 24 (Day 51), 48 (Day 52), and 168 (Day 57) hours after the last dose, and at the follow-up visits on Day 64 and Day 85. A maximum of 3 samples may be collected at additional time points during the study if warranted and agreed upon by both the investigator and sponsor.
- l These tests will be performed or stored at the central laboratory or Lilly-designated laboratory.

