Preliminary data have shown that there has been no apparent concentration-dependent increase in systolic or diastolic blood pressure (BP) after single or multiple doses; however, there was an increase in heart rate in the MAD portion of the study.

LY3298176 PK was studied across a range of doses administered as single doses or multiple doses (4 doses) via a once-weekly dosing regimen. Based on preliminary data, LY3298176 PK appeared linear and dose proportional during the dose range studied. Peak concentrations were observed at 1 to 2 days postdose, and the half-life was approximately 5 days.

In conclusion, based on preliminary data, PK profile of LY3298176 supports once-weekly SC dosing, and there were no safety concerns to preclude further clinical development.

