Patients in Cohort 1 will receive either LY3298176 with titration regimen starting from 2.5 mg for Days 1 and 8 followed by 5 mg for Days 15 and 22, and 10 mg for Days 29, 36, 43, and 50, or corresponding volume-matched placebo. Patients in Cohort 2 will receive either LY3298176 with titration regimen starting from 5 mg for Days 1 and 8 followed by 10 mg for Days 15, 22, 29, and 36, and 15 mg for Days 43 and 50, or corresponding volume-matched placebo. Patients in Cohort 3 will receive either 5 mg LY3298176 or placebo for 8 weeks (Section 5.5). The planned highest dose or dosing regimen of Cohort 2 may be changed for the reason of tolerability (Section 7.4).

If the investigator decides not to up-titrate the dose level of IMP for individual patients in the titration regimen in Cohorts 1 or 2 for the reason of safety and/or tolerability, patients may keep current dose level to the planned last dose at Day 50 and will no longer be allowed up-titration during the treatment period. Down-titration is not allowed during the treatment period for any patients in Cohorts 1, 2, or 3.

Safety, as assessed by AEs, vital signs, 12-lead ECGs, concomitant medications, safety laboratory measurements, and medical assessments from at least 8 patients (to include at least 5 on LY3298176) up to Day 36 predose procedure of Cohort 1, will be reviewed by the sponsor and investigator before dose-escalation decision to Cohort 2 (Section 7.4.1).

Dosing will be staggered in Cohorts 1 and 2 so that an initial group of up to 6 patients receiving LY3298176 and 2 patients receiving placebo will be dosed. On Days 4 and 32 of Cohort 1 and on Days 4, 18, and 46 of Cohort 2, the investigator and Lilly clinical pharmacologist, clinical research physician (CRP), or clinical research scientist (CRS) will review available safety data from these patients, and if no relevant safety signals are noted, the remaining patients will be dosed. Patients in Cohort 3 will be dosed after evaluation of safety data of the initial staggered group of Cohort 2.

PK sampling and safety assessments, including AEs, concomitant medications, medical assessments, clinical laboratory tests, vital signs, and ECGs, will be performed according to the Schedule of Activities (Section 2).

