9.4.4. Safety Monitoring

The Lilly clinical pharmacologist, CRP, or CRS will monitor safety data throughout the course of the study.

Lilly will review SAEs within time frames mandated by company procedures. The Lilly clinical pharmacologist, CRP, or CRS will periodically review the following data:

- trends in safety data
- laboratory analytes
- serious and nonserious AEs, including AEs of special interest (for example, GI events, hypoglycemia, injection-site reactions, and hypersensitivity reactions) and reported and adjudicated pancreatitis

When appropriate, the Lilly clinical pharmacologist, CRP, or CRS will consult with the functionally independent Global Patient Safety therapeutic area physician or clinical research scientist.

In the event that safety monitoring uncovers an issue that needs to be addressed by unblinding at the group level, additional analyses of the safety data will be conducted by the personnel included in the Blinding/Unblinding Plan ([Appendix 8](#)).

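### If Cohort 2 switches to the 2.5/5/8 mg regimen, its first 8 mg dose (Day 29) has no scheduled 24–72 h assessment, because the inpatient block and group review stay on Days 43–46

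*Protocol*

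**What the plan says.** Protocol 7.4.1 (Dose Escalation) pre-authorises a second regimen for Cohort 2: 2.5 mg on Days 1 and 8, then "5 mg for Days 15 and 22; and 8 mg for Days 29, 36, 43, and 50, or the corresponding volume-matched placebo". The switch is allowed only when the Cohort 1 safety review finds 10 mg poorly tolerated, and it must be made ahead of any Cohort 2 dosing. The planned regimen is 5, 10 and 15 mg, with steps on Days 15 and 43.

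Protocol 5.1 fixes the group safety reviews: "On Days 4 and 32 of Cohort 1 and on Days 4, 18, and 46 of Cohort 2". SAP Section 5 repeats these days. Both sections note that the Cohort 2 regimen may change, but neither attaches a change of review or visit days to it.

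Protocol Section 2 has one Cohort 2 table, "Study Schedule Protocol I8F-JE-GPGC Cohort 2 for Treatment Period". It marks up-titration on Days 15 and 43 and has inpatient blocks on Days -1 to 4, 15–18, 43–46 and 50–52. Day 29 (±1) is an outpatient visit with predose procedures only, and the next column is Day 36 (±1).

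The corresponding table for Cohort 1, "Study Schedule Protocol I8F-JE-GPGC Cohort 1 for Treatment Period", does have a Day 29–32 block, because Cohort 1 steps up on Day 29.

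**The concern.** Each planned up-titration in Cohorts 1 and 2 is followed by a 24–72 h inpatient block, with either a group review or the pre-discharge safety review close to it. The alternative regimen moves the last step from Day 43 to Day 29 but leaves the block and the last review where they were. They then fall on a dose that has not changed, and the real step is taken as an outpatient.

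Protocol 3.2 says "Peak concentrations were observed at 1 to 2 days postdose, and the half-life was approximately 5 days", so the unobserved interval includes the peak after the step. The alternative is used only when tolerability at 10 mg has already been a problem. Down-titration is not allowed, so the choice for a patient who does poorly on the first 8 mg dose is to redose at 8 mg on Day 36 or to stop. Early observation informs that choice.

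**Working it through.** **1. Dose steps against the Cohort 2 schedule**

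Inputs: step days from Protocol 5.1 and 7.4.1; visit columns from the Section 2 Cohort 2 table (Days -1, 1–4, 8, 15–18, 22, 29, 36, 43–46, 50–52, 57); review days 4, 18 and 46 from 5.1.

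| Regimen | Step day | Visits 1–3 days later | Next visit | Next group review |
|---|---|---|---|---|
| Planned | 1 | 2, 3, 4 | 2 | 4 |
| Planned | 15 | 16, 17, 18 | 16 | 18 |
| Planned | 43 | 44, 45, 46 | 44 | 46 |
| Alternative | 1 | 2, 3, 4 | 2 | 4 |
| Alternative | 15 | 16, 17, 18 | 16 | 18 |
| Alternative | 29 | none | 36 | 46 |

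Only the Day 29 step is uncovered.

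- Postdose checks: the planned Day 43 step has vital signs at 24, 48 and 72 h and safety labs at 24 and 48 h. The alternative Day 29 step has none of these.
- Time to next visit: 36 − 29 = 7 days, or 168 h. This is the same predose convention that schedule footnote k uses after the first dose ("168-hour sample to be collected before the second dose of LY3298176"). Doses must be at least 6 days apart, so the dosing visit cannot come earlier than 6 days.
- Time to group review: 46 − 29 = 17 days (16 to 18 with the ±1 day window), after 8 mg doses on Days 29, 36 and 43. Under the planned regimen it is 46 − 43 = 3 days, after one dose.

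**2. Where the exposure change falls**

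Assumptions: linear superposition and a 5-day half-life. The load just after dose n is L_n = dose_n + L_(n−1) × 2^(−7/5), and the weekly carry-over 2^(−7/5) is 0.379.

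- Alternative regimen, Days 1 to 50: 2.50, 3.45, 6.31, 7.39, 10.80, 12.09, 12.58, 12.77 mg.
- Day 22 to Day 29: 10.80 / 7.39 = 1.46, a rise of 46%.
- Day 36 to Day 43: 12.58 / 12.09 = 1.04, a rise of 4%.
- Planned regimen, Day 36 to Day 43: 21.03 / 15.91 = 1.32, a rise of 32%.
- Cohort 1 on Day 29: 12.80 mg. The alternative is lower by 1 − 10.80 / 12.80 = 16%.

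Protocol 3.2 gives mean half-lives of 109 to 123 h in healthy subjects. Over that range the Day 29 rise is 46–47% and the Day 43 rise is 3–4%. Under the alternative, the block stays where load hardly changes and is absent where it rises.

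**The case against.** The mismatch itself is hard to dispute; the case against it concerns importance.

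- **It is a fallback.** The planned regimen is unaffected. The alternative applies only if 10 mg is poorly tolerated and none of the 7.4.1 rules that end escalation is met. The switch is agreed before Cohort 2 starts, and the table visibly marks up-titration on Day 43, so the team might well correct it. This stands as a limit. But 7.4.1 requires agreement on the dose, not on a new schedule. Table GPGC.2 also has no 8 mg row, which suggests the option was not carried through the document.
- **Exposure is lower than in Cohort 1.** Doses match Cohort 1 up to Day 22 and are 8 instead of 10 mg after that. In the model above, the highest alternative load (12.77 mg, Day 50) does not exceed Cohort 1's first 10 mg load (12.80 mg), which was observed as an inpatient. In mg, the Day 29 step is 10.80 − 7.39 = 3.41, against 21.03 − 15.91 = 5.12 for the planned Day 43 step. Titrated 8 mg was also better tolerated than a single 8 mg dose in Study GPGA. All of this stands.
- **Other monitoring continues.** Adverse events are recorded, the sponsor's clinical pharmacologist or physician "will monitor safety data throughout the course of the study", unscheduled vital signs and ECGs are allowed, and Day 36 predose includes vital signs, ECG and labs. Stays may be extended at the investigator's discretion, but that power is tied to a planned discharge day, and Day 29 is an outpatient visit. None of this is a scheduled 24–72 h assessment.
- **The group reviews cover the initial staggered group**, up to 6 patients on LY3298176. The 17-day figure therefore describes that group. The missing 24–72 h visits affect everyone in the cohort.

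**Conclusion.** The concern holds. If the 2.5/5/8 mg regimen is adopted and the documents are followed as written, up to 16 LY3298176 patients take their first 8 mg dose with no scheduled assessment at 24–72 h and one scheduled assessment in the following 7 days. For the initial staggered group, the next group review is 17 days and three doses after the step, instead of 3 days and one dose.

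The visit and review counts come directly from the schedule and need no model. The exposure figures rest on linear superposition and the stated half-life; they only illustrate that the step is at Day 29 and not at Day 43. Under the alternative, 8 mg is still observed at 24–72 h after Day 43 and again after Day 50, but not at first exposure.

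This is a contingent safety-monitoring inconsistency of moderate importance. It should be fixed. It does not affect the planned 5/10/15 mg regimen or any analysis.

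**What to change.** Add to Protocol 7.4.1, 5.1 and Section 2, and to SAP Section 5 for the review days, that if the alternative Cohort 2 regimen is used:

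- the inpatient stay and postdose assessments of Days 43–46 move to Days 29–32, as in the Cohort 1 schedule;
- Day 43 becomes an outpatient, predose visit;
- the Day 46 group review moves to Day 32;
- the Day 4 and Day 18 reviews and the Day 50–52 block stay as they are.

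The Cohort 1 table already gives Day 29 without a window and Day 43 with ±1 day, so those windows can be taken over too. No dose or titration rule changes.

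The cost is protocol wording. One four-day block moves and none is added, so inpatient nights are unchanged. What is lost is the 24–72 h observation after the Day 43 dose. The Day 50–52 block still observes 8 mg at nearly the same modelled load (12.77 against 12.58 mg), with 24 and 48 h labs and 8 and 24 h ECGs, but without 24–72 h vital signs. Postdose PK sampling is unaffected, because footnote k schedules it only after the first and last doses.
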